Reason for treatment discontinuation	Chart review	Treatment characteristics	Study observation period	
Data for discontinuation reason will exclusively come from chart review. Reviewers will be asked to select reason(s) as explicitly documented in patients' charts. If available, reason patients discontinued treatment will be abstracted:
 
 
Progression
 
Toxicity
 
Decline in performance status
 
Financial/insurance
 
Completed planned treatment
 
Death
 
Hospice
 
Patient preference (if other categories do not apply)
 

PFIZER CONFIDENTIAL

				Physician preference (if other categories do not apply) Other
Proportion of patients who advance/do not advance	iKM structured data + chart review (derived)	Treatment characteristics	Study observation period	The proportion of patients who advance and do not advance from the index treatment will be summarized as the count and percentage of the following: Patients with ongoing index treatment Patients who died following index treatment Patients who advanced to a subsequent treatment Patients who did not advance to a subsequent treatment for unknown reasons
Post-index treatment regimen	iKM structured data + chart review	Treatment characteristics	Study observation period	The regimen received by patients following discontinuation from the index treatment.
Time to chemotherapy	iKM structured data +chart review (derived)	Clinical outcomes	Study observation period	Time to chemotherapy will be defined as the interval (in weeks) between index treatment and start of chemotherapy as documented in the iKM EHR database. Patients with ongoing treatment at the study observation period will be censored on the study end date or the last visit date available in the dataset, whichever occurred first. rwDOT will be analyzed using the Kaplan-Meier method with 95% CIs, and summary tables of the number of events and censored patients at 6, 12, 18, 24, 30, and 36 months.

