### Clinical outcomes

Time-to-event outcomes, time to chemotherapy, rwDOT, TTNT, OS, rwTTP and rwPFS, will be assessed using the Kaplan-Meier method with 95% CIs, and summary tables of the number of events and censored patients at 6, 12, 18, 24, 30, and 36 months among those who initiated first-line PB+FUL. Further details about these calculations are presented in **Table 2**.

CCI

To reduce the effect of selection bias, the study team will first consider baseline variables/covariates compared among propensity score matched cohorts. The propensity score, defined as the probability of being initiated on PB+FUL treatment, will be estimated using a multivariate logistic regression model conditional on the baseline covariates (e.g., age, gender, ethnicity, body mass index (BMI), menopausal status, comorbidities, ECOG, stage of diagnosis, count of metastatic sites and site of metastases). Each individual will have a propensity score that represents the probability of being treated with PB+FUL. Pairs of treated and untreated subjects will be matched on the logit of the propensity score using a caliper of width equal to 0.2 of the standard deviation of the logit of the propensity score, as this caliper has been shown to be optimal in a range of settings.

Alternatively, if propensity score matching is not supported by the sample size, standardized or normalized inverse probability of treatment weighting (IPTW) using propensity score may be applied to balance baseline demographic and clinical characteristics between the 2 comparison cohorts. For standardized IPTW, the propensity score weight will be calculated as the inverse of the propensity score (1/propensity score), then create a weight reflect the sample size for each of the treatment groups, i.e.,  $(1/\text{propensity score}) * (\text{number of obs. in treatment A}) / (\text{number of obs. in entire study group})$ . For normalized IPTW, the weights will be calculated as the inverse of patients' estimated probability of being in treatment. Finally, the normalized weights will be calculated by dividing each weight by the overall mean weight. After weighting, the sum of weights attributed to each patient in a given cohort may not be equal to the sample size of this cohort, consequently, the effective sample size after weighting may be different than the original sample size (i.e., before weighting), although the total size of whole study population will not be changed.

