## **8.9. Limitations of the research methods**

### **8.9.1. Internal validity of study design**

#### **Measurement error(s)/misclassification(s)**

This observational and retrospective study uses iKM EHR data. The iKM database is not collected for research purposes but for clinical practice reasons. This may impede the standardization of the data collection methods and instruments and the reporting practices of the physician. As with all administrative databases, iKM data are subject to coding errors of omission and commission. Problems with inadequate or inaccurate codes in the databases may introduce some level of misclassification bias of certain diagnoses, events, or procedures of interest. Likewise, some variables of interest may not be as complete across the entire population. The iKM EHR contains information on patients only when they are seen by USON physicians. Services and procedures provided outside of the USON are not captured by the database, as well as drugs received by patients from pharmacies not affiliated with USON practices.

A patient's treatment history prior to his/her first encounter at a USON practice may be only available in physician progress notes and is not well captured in the iKM EHR. We cannot rule out the possibility that some patients coded as receiving being treatment naïve for metastatic disease in iKM EHR actually had previous chemotherapy for metastatic disease in healthcare facilities outside the USON.

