5 ENDPOINTS AND COVARIATES

5.1 EFFICACY/EFFECTIVENESS ENDPOINT(S)

Time to chemotherapy

[figure not shown]
Time to chemotherapy will be defined as the interval (in weeks) between index treatment and start of chemotherapy as documented in the iKM EHR database. Patients with ongoing treatment at the study observation period will be censored on the study end date or the last visit date available in the dataset, whichever occurred first. rwDOT will be analyzed using the Kaplan-Meier method with 95% CIs, and summary tables of the number of events and censored patients at 6, 12, 18, 24, 30, and 36 months.

Reason for treatment discontinuation

Data for discontinuation reason will exclusively come from chart review. Reviewers will be asked to select reason(s) as explicitly documented in patients' charts.

Real-world duration of treatment (rwDOT)

PFIZER CONFIDENTIAL

rwDOT will be defined as the interval (in weeks) between the start and stop index as documented in the iKM EHR database. Patients with ongoing treatment at the study observation period will be censored on the study end date or the last visit date available in the dataset, whichever occurred first. rwDOT will be analyzed using the Kaplan-Meier method with 95% CIs, and summary tables of the number of events and censored patients at 6, 12, 18, 24, 30, and 36 months.

Time to next treatment (TTNT)

TTNT will be defined as the interval (in weeks) between the start of the index treatment and the date of the next-line treatment as documented in the iKM EHR database. Patients who did not advance to the next treatment within the study observation period will be censored on the study end date or the last visit date available in the dataset, whichever occurred first. TTNT will be analyzed using the Kaplan-Meier method with 95% CIs, and summary tables of the number of events and censored patients at 6, 12, 18, 24, 30, and 36 months.

Provider-documented progression

The proportion of patients with provider-documented progression will be reported.

Real-world time to tumor progression (rwTTP)

The rwTTP will be measured from the initiation the index treatment to the date of provider-documented progression, censoring patients without evidence of provider-documented progression at the last visit date. The rwTTP will be estimated in weeks using the Kaplan-Meier method with 95% CIs, and summary tables of the number of events and censored patients at 6, 12, 18, 24, 30, and 36 months.

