Reason for treatment discontinuation	Chart review	Treatment characteristics	Study observation period	
Data for discontinuation reason will exclusively come from chart review.
 
Reviewers will be asked to select reason(s) as explicitly documented in patients' charts.
 
If available, reason patients discontinued treatment will be abstracted:
 
Progression Toxicity Decline in performance status Financial/insurance Completed planned treatment Death Hospice Patient preference (if other categories do not apply) Physician preference (if other categories do not apply) Other

PFIZER CONFIDENTIAL

Proportion of patients who advance/do not advance	iKM structured data + chart review (derived)	Treatment characteristics	Study observation period	
The proportion of patients who advance and do not advance from the index treatment will be summarized as the count and percentage of the following:
 
Patients with ongoing index treatment
 
Patients who died following index treatment
 
Patients who advanced to a subsequent treatment
 
Patients who did not advance to a subsequent treatment for unknown reasons

Post-index treatment regimen	iKM structured data + chart review	Treatment characteristics	Study observation period	The regimen received by patients following discontinuation from the index treatment.
Time to chemotherapy	iKM structured data + chart review (derived)	Clinical outcomes	Study observation period	Time to chemotherapy will be defined as the interval (in weeks) between index treatment and start of chemotherapy as documented in the iKM EHR database. Patients with ongoing treatment at the study observation period will be censored on the study end date or the last visit date available in the dataset, whichever occurred first. rwDOT will be analyzed using the Kaplan-Meier method with 95% CIs, and summary tables of the number of events and censored patients at 6, 12, 18, 24, 30, and 36 months.

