Real-world complete, improved or stable	Chart review (derived)	Clinical outcomes	Study observation period	
In real-world research, the parameters underlying response as defined by RECIST criteria are often unavailable. As such, this

PFIZER CONFIDENTIAL

disease rate (clinical benefit rate)				study will assess response to treatment as documented by providers and capture real-world assessments of response, including complete response, improved disease and stable disease. This measure will be similar to clinical benefit rate as defined by RECIST criteria.
Clinical outcomes				
Last USON visit date	iKM structured data + chart review	Clinical outcomes	Study observation period	Each patient's most recent visit date, prior to or on close of study observation period will be recorded. A visit is defined as a physician encounter with the practice where either treatment is given or vital signs are recorded. For patients with a death date, this last visit date should occur prior to the death date. This will not be reported separately; it will be used in calculating the patient's available follow-up time as a descriptive measure. available follow-up time = Integer (latest of last visit date or death date – index date +1)
Death date	iKM structured data, chart review + external sources	Clinical outcomes	Study observation period	Date of death will be captured from the iKM EHR, limited access death master file (LADMF), national death index (NDI) and, possibly, other commercial sources of death information (the study team is confirming the utility of these sources). If dates conflict among the sources, the NDI, followed by the LADMF date will be prioritized. If severe data discordance is observed (i.e., death is reported to occur prior to the index date), then the iKM death date will be used. Further information on the sources of death information is presented in Section 2.1.2 .
Follow-up duration	iKM structured data, chart review + external sources (derived)	Clinical outcomes	Study observation period	The duration between index and last follow-up date. Findings will be summarized as the mean (\pm SD) and median (range) for all patients within the specified cohort. The number of patients with available data will be reported.

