7.2.2 Summary of Analyses

Table 2 presents an overview of the planned analyses for this study. As supported by the final sample size, each of the results tables and figures will be stratified to present the data for the stratifications defined in **Section 4.4**.

Table 2. Overview of study analyses

Analysis	Data source	Statistical method	Missing data
Baseline demographic and clinical characteristics	Structured + chart review data	Descriptive statistics	Missing values reported
Provider- and clinic-level characteristics	Structured data only	Descriptive statistics	Missing values reported
Treatment patterns	Structured + chart review data	Descriptive statistics	Missing values reported
Time to chemotherapy	Structured + chart review data	Kaplan-Meier methods	Patients without the event will be censored
Real-world duration of therapy (rwDOT)	Structured + chart review data	Kaplan-Meier methods	Patients without the event will be censored
Time to next treatment (TTNT)	Structured + chart review data	Kaplan-Meier methods	Patients without the event will be censored
Overall survival (OS)	Structured data + chart review data + LADMF/NDI	Kaplan-Meier methods	Patients without the event will be censored
Real-world time to tumor progression (rwTPP)	Structured data + chart review data + LADMF/NDI	Kaplan-Meier methods	Patients without the event will be censored
Real-world progression-free survival (rwPFS)	Structured data + chart review data + LADMF/NDI	Kaplan-Meier methods	Patients without the event will be censored

[figure not shown]
PFIZER CONFIDENTIAL

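### TTNT and time to chemotherapy censor patients who die first; their Kaplan-Meier curves and medians are a valid cause-specific display but, read as the real-world share or timing, are too high and too early

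*SAP*

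**What the plan says.** **TTNT** (SAP 5.1 and Table 1; Protocol Table 2). The only event is the start of next-line treatment. "Patients who did not advance to the next treatment within the study observation period will be censored on the study end date" or at the last visit, whichever is earlier. Because the last visit should precede any death date (SAP Table 1, last USON visit date), a patient who dies before the next line is censored before the death.

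**Time to chemotherapy** (same places). "Time to chemotherapy will be defined as the interval (in weeks) between index treatment and start of chemotherapy". The rule then gives a censoring date for one group only: "Patients with ongoing treatment at the study observation period will be censored on the study end date or the last visit date", whichever is earlier. It does not mention death or patients who are off index treatment. Its analysis sentence names another endpoint: "rwDOT will be analyzed using the Kaplan-Meier method with 95% CIs".

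**SAP Table 2** (7.2.2). For both endpoints, "Patients without the event will be censored". This brings deaths before chemotherapy into the censored group. The listed sources are structured and chart review data, without the death registries.

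**Estimator.** Protocol 8.7.3: "Time-to-event outcomes, time to chemotherapy, rwDOT, TTNT, OS, rwTTP and rwPFS, will be assessed using the Kaplan-Meier method with 95% CIs". The readable text has no competing-risk method and no statement of what the curve estimates. Redacted blocks may say more.

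**Related provisions.** rwPFS counts death as an event (SAP 5.1). A descriptive table gives crude percentages of patients ongoing, died and advanced (SAP Table 1). Rates at 6-36 months are defined for OS and rwPFS only.

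**The concern.** A patient who dies before next treatment or chemotherapy can no longer have the event. Kaplan-Meier treats that patient as someone who could still have had it after leaving the risk set. One minus Kaplan-Meier then describes what would be seen if death did not remove patients, and only if death is unrelated to the event.

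The study's purpose is to describe real-world treatment patterns. A reader of a TTNT or time-to-chemotherapy curve, or its median, is likely to take it as how many patients moved on and when. On that reading the error always goes one way, and nothing in the readable text warns against it.

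A smaller point sits beside this. The time-to-chemotherapy paragraph carries over the rwDOT wording. Its censoring date therefore depends on being on treatment, although a patient can stop PB+FUL or switch to a non-chemotherapy regimen and remain chemotherapy-free.

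**Working it through.** The plan gives no expected rate, event count or precision for either endpoint, so there is no figure to reproduce.

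**Direction.** Let l(u) be the hazard of the event, h(u) the hazard of death first, and L and H their cumulative forms.

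- One minus Kaplan-Meier, deaths censored, targets ∫ l(u) exp(-L(u)) du.
- Cumulative incidence is ∫ l(u) exp(-L(u) - H(u)) du.

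Since exp(-H) is at most 1, the first is never below the second, whatever the hazards.

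**Size under constant hazards.**

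- 1-KM = 1 - exp(-l t)
- CIF = l/(l+h) × [1 - exp(-(l+h) t)]

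Inputs, all assumptions for this cohort:

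- Death-first rate h: 0.1%, 0.32% or 0.64% per month. The top value is all-cause mortality from the three-year OS of 79.4% quoted in SAP 2: -ln(0.794)/36 = 0.0064. It includes deaths after the event. 0.32% is half of it.
- Median, with l = ln 2/median: TTNT 12-24 months; chemotherapy 24-48 months.

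Worked cases at 36 months, h = 0.0032:

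- TTNT, median 18: l = 0.0385. 1-KM = 75.0%. CIF = 0.0385/0.0417 × [1 - exp(-1.501)] = 71.8%. Excess 3.2 points.
- Chemotherapy, median 36: l = 0.01925. 1-KM = 50.0%. CIF = 0.01925/0.02245 × [1 - exp(-0.808)] = 47.5%. Excess 2.5 points.

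Excess of 1-KM over cumulative incidence, in percentage points:

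| Endpoint (assumed median) | Month | h = 0.1% | h = 0.32% | h = 0.64% |
|---|---|---|---|---|
| TTNT (12-24) | 12 | 0.2-0.3 | 0.5-0.8 | 1.0-1.7 |
| TTNT (12-24) | 24 | 0.5-0.7 | 1.7-2.2 | 3.2-4.3 |
| TTNT (12-24) | 36 | 1.0-1.1 | 3.0-3.3 | 5.8-6.4 |
| Chemotherapy (36) | 12 | 0.1 | 0.4 | 0.7 |
| Chemotherapy (36) | 24 | 0.4 | 1.3 | 2.5 |
| Chemotherapy (24-48) | 36 | 0.7-1.0 | 2.1-3.0 | 4.0-5.8 |

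Time by which half of patients have actually had the event, at the three rates:

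- TTNT: 18.2, 18.7 or 19.5 months, against a Kaplan-Meier median of 18.
- Chemotherapy: 36.9, 39.0 or 42.8 months, against 36.

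**Higher mortality.** The five-year survival of 27% for distant disease quoted in SAP 2 implies -ln(0.27)/60 = 0.0218, about 2.2% per month from all causes. With death first at 5-15% per year (about 0.4-1.4% per month), the 36-month excess is 3.9-12.7 points for TTNT (medians 12-24) and 2.3-9.3 for chemotherapy (medians 36-60).

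**Deaths after contact is lost.** A simulation assumed 47 months of uniform accrual, cut-off at month 53, h = 0.32%, monthly visits, 1% or 2% monthly loss from the network, 2% monthly death after the event, and every death captured. For 36-month TTNT (median 18, truth 71.8%) it gave:

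- 1-KM: 75.7% at both loss rates.
- Cumulative incidence counting every registry death: 69.8% or 66.9%.
- Counting only deaths within 3 months of the last visit: 72.3% or 72.1%; within 6 months: 72.1% or 71.8%.
- With visits 3 months apart, the 3-month window: 73.4% or 73.8%, still 1.6-2.0 points high.

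**The case against.** **The outputs exposed are few.** Landmark percentages are defined for OS and rwPFS only. For these two endpoints the 6-36-month tables give numbers of events and censored patients, which are not biased, and the crude table shows deaths apart from patients who advanced. This stands, and it limits the point to the curve and the median. A reader might infer that a biased 36-month percentage is planned; the documents do not specify one, and the table shells are not visible. The crude table helps only in part: it is not by time and does not cover chemotherapy.

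**Kaplan-Meier is not wrong in itself.** This stands. A reader might infer that the estimator is invalid. It is a proper cause-specific display; what is missing is the label and the companion estimate.

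**The chemotherapy censoring date is not undefined.** A reader might infer that the date is left entirely open. SAP 2.1.1 and Protocol 8.2 follow patients to study end, last visit or death, whichever is first, and an analyst would fill the gap from there. That rule is not tied to the endpoint, so a correction is due, but only to wording. The misplaced rwDOT name does no harm either, since Kaplan-Meier for time to chemotherapy is stated in Protocol 8.7.3 and SAP Table 2.

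**The size is assumed and may be modest against sampling error.** It is assumed. In the simulation above (317 patients) the TTNT gap was 75.7 - 71.8 = 3.9 points. The standard error of the 3-month-window estimate was 3.6-4.0, so the shift is about one standard error. It is systematic and does not shrink with more patients.

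**rwTTP also censors deaths.** True, but rwPFS stands beside it and counts them. TTNT and time to chemotherapy have no such companion by time.

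**Conclusion.** The point holds as a cheap improvement to two secondary, descriptive endpoints. Patients who die first are censored: by TTNT's own rule, and by SAP Table 2 for time to chemotherapy. The resulting curve and median overstate how many patients reach the event, and how soon, if read as real-world share or timing.

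The direction is certain against cumulative incidence. It would reverse against a composite of next treatment or death, which is a further reason to state the target. The size is not in the documents. Under the constant rates of 0.1-0.64% per month it is about 1-6 points for TTNT and 0.7-6 points for chemotherapy at 36 months, at most 1.7 points for TTNT at 12 months, and larger if mortality is higher.

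The documents do not support saying that the planned counts are biased, that Kaplan-Meier is invalid, or that one death window would remove the bias. The finding is limited to the readable text.

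**What to change.** 1. **Label and add.** For TTNT and time to chemotherapy, keep Kaplan-Meier and label it *deaths censored; not the share of patients treated*. Add Aalen-Johansen cumulative incidence at 6, 12, 18, 24, 30 and 36 months, with death before the event as a competing event. Use the death dates already collected for OS, and list LADMF and NDI as sources for both endpoints in SAP Table 2.

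2. **Show sensitivity to late deaths.** Protocol 8.9.1 says "Services and procedures provided outside of the USON are not captured by the database", while deaths also come from registries. A patient can therefore be treated elsewhere unseen and still be recorded as having died. Report the cumulative incidence counting all deaths, and counting only deaths within pre-specified windows after the last visit, such as 3 and 6 months. No single window should be presented as unbiased.

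3. **Correct the wording.** In the time-to-chemotherapy text (SAP 5.1, SAP Table 1, Protocol Table 2), replace the copied rwDOT sentences. All patients without chemotherapy are censored at the earlier of last visit or study end, whatever their index-treatment status, in line with the follow-up rule in SAP 2.1.1 and Protocol 8.2. The exception is that deaths count as competing events in the cumulative-incidence analysis. Name time to chemotherapy in the analysis sentence.

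**Cost.** Extra tables, revised shells and standard SAS or R code; a judgement on late deaths, handled by the sensitivity analysis; and a protocol update with IRB re-submission, which the Protocol 8.7 footnote requires when the SAP is modified. No new data are needed.
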